## ABSTRACT

Depression is present in about 20-30% of hemodialysis patients and is associated with morbidity and mortality. However, depression is inadequately diagnosed and treated among dialysis patients. This is due in part to the overlap between depressive symptoms (e.g. appetite change, trouble sleeping, feeling tired) and symptoms related to persistent metabolic derangements in hemodialysis patients (e.g. nausea, nocturnal cramps, feeling washed out after treatment). The overlap between depressive symptoms and dialysis-related complications makes it difficult to diagnose and therefore to treat depression. In addition, prescription of antidepressant medication may increase an already high pill burden and result in poor adherence. Moreover, the evidence base to guide depression treatment among hemodialysis patients is limited. In our previous work, we developed methods to use latent variables and structural equation modeling to isolate depressive symptoms. Other investigators have demonstrated that directly observed treatment enhances the effectiveness of tuberculosis and HIV treatment.

We now propose a cross-sectional study (Phase 1) followed by a randomized controlled trial (Phase 2) at 17 dialysis facilities. The cross-sectional study will involve assessments of depressive symptoms (using the PHQ-9 screening instrument) as well as dialysis-related complications (KDQOL) in about 1083 patients. We will then use structural equation modeling to develop and validate a hemodialysis-specific PHQ-9 (hdPHQ-9) that will isolate depressive symptoms. The trial will involve 216 patients with confirmed depression who will be randomly assigned to (a) directly observed weekly antidepressant treatment with fluoxetine or (b) referral to their nephrologists, their primary care physicians, or nearby mental health providers. The primary outcome of the trial will be remission of depression at 12 weeks. The trial results will also be used to compare the responsiveness of the PHQ-9 and the hdPHQ-9. We anticipate that the hdPHQ-9 will be a valid and responsive instrument that will isolate depressive symptoms in hemodialysis patients and ultimately improve the screening and diagnosis of depression. We also expect that directly observed weekly fluoxetine treatment will be an effective way to manage depression among hemodialysis patients.

Innovative features of the proposed project include the use of latent variables to address overlap, administration of a long acting weekly antidepressant, directly observed treatment, and a rigorous randomized controlled trial design. The project has the potential not only to improve the diagnosis and management of depression among hemodialysis patients but also to improve their morbidity and mortality. Furthermore, it may serve as a model for future studies to isolate symptoms among overlapping medical conditions.

[figure not shown]

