### Study design overview and timetable

After a development and training period, we propose a cross-sectional study followed by a randomized controlled trial. The cross-sectional study will involve assessments of depressive symptoms (PHQ-9) and quality of life for **1083 patients**. These data will be used to address Aim A (diagram above). The trial will involve **216 patients** with DSM5-confirmed depression who will be assigned to **2 groups** using envelopes for randomization.

- Approximately 108 patients will be randomized into the intervention/fluoxetine group over the duration of the entire study. Patients randomized to fluoxetine will be prescribed 2 weeks of short-acting fluoxetine 20 mg and will be instructed to take the prescription daily for 2 weeks. After the approximately 2 weeks of daily fluoxetine is completed, patients will receive a filled prescription of long-acting fluoxetine 90 mg to be taken weekly (observed during dialysis) for 10 additional weeks. The first dose of fluoxetine 90mg will be 5-8 days after the last dose of daily 20mg fluoxetine based on FDA guidelines. During each week, the nurse practitioner or research assistant will review possible adverse effects and response to treatment. At the end of the 12-week study period, participants will be provided 4 additional weeks of 90 mg fluoxetine in order to provide sufficient time to follow up with their primary care physician or nephrologist.
- Approximately 108 patients will be randomized into the control/referral group over the duration of the study. Patients randomized to referral will be informed about their diagnosis and asked to follow-up with their nephrologists or primary care physicians and will also be given a list of nearby mental health providers. Details about their study

evaluation will be shared with their nephrologists, primary care physicians, and any mental health providers.

- After 12 weeks, patients in both groups will undergo repeat assessments of the PHQ-9, KDQOL, and DSM5 structured diagnostic interview. These data will be used to address Aims B and C.

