We anticipate beginning the project at 2-3 dialysis facilities and estimate it will take about 4-5 months to complete the cross-sectional study and randomized controlled trial at these facilities. We will then involve another 2-3 facilities in the project. This process will continue until we reach our target sample size. Based on our previous work, we anticipate that it will take approximately 45 months to complete the trial. We considered involving more study personnel to shorten the time necessary to complete the trial but felt that this would impair our ability to maintain study quality and intervention fidelity. Intervention fidelity will be maintained through initial training, in-person meetings, monitoring of study notes, and direct observation. Trial results will be reported in accordance with CONSORT recommendations.

Note that we will use the PHQ-9 and the DSM5 structured interview to screen for depression, confirm the diagnosis, and determine response to treatment. While the overlap between dialysis complications and depressive symptoms may affect the accuracy of these methods, they are currently standard practice in depression intervention trials. **Until we have assessed the validity and responsiveness of the hemodialysis-specific PHQ-9 (hdPHQ-9), it would be premature to use this new instrument for screening or for determining response to treatment.**

Year	1	1	1	1	2	2	2	2	3	3	3	3	4	4	4	4	4	5	5	5
Quarter	1	2	3	4	1	2	3	4	1	2	3	4	1	2	3	4	1	2	3	4
DEVELOPMENT & TRAINING																				
Finalize study protocol, instruments	x	x																		
Train study personnel	x	x																		
Refine conceptual model	x	x																		
RANDOMIZED CONTROLLED TRIAL					x	x	x	x	x	x	x	x	x	x	x	x	x	x	x	
Recruit eligible patients			x	x	x	x	x	x	x	x	x	x	x	x	x	x	x	x	x	
Baseline evaluation		x	x	x	x	x	x	x	x	x	x	x	x	x	x	x	x	x	x	
Fluoxetine vs. referral trial		x	x	x	x	x	x	x	x	x	x	x	x	x	x	x	x	x	x	
Final evaluation		x	x	x	x	x	x	x	x	x	x	x	x	x	x	x	x	x	x	
ANALYSIS & MANUSCRIPTS																	x	x	x	x
Develop, validate new screening instrument																	x	x	x	x
Impact of directly observed weekly fluoxetine																		x	x	x
Responsiveness of new instrument																		x	x	x

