## **Data elements**

Baseline (week 0) and final (week 12) data on patient characteristics, PHQ-9 and KDQOL will be obtained by a research assistant. Patients will be interviewed during dialysis to obtain the data elements listed below. In previous trials, we found that many patients are unable to complete self-administered questionnaires such as the PHQ-9 because of visual problems or low health literacy. Other patients are not allowed to move their dominant arm during dialysis treatment because tubing from the dialysis machine is connected to blood vessels in the arm. The combination of sitting next to the patient and the ambient noise in the dialysis facility allows for a relatively private interview. If patients prefer, they may be interviewed in a separate room following completion of dialysis treatment. It is not possible to blind study personnel to assessments of depression treatment, adherence, response, and adverse effects during the trial (day 3, weeks 1, 2, 4, 6, 8, 10). Patients will be given a \$20 clincard at the end of each interview to thank them for participation. The nurse practitioner and other study team members will have a lock box for transporting consent and clincard receipts. Other study documents will be devoid of PHI. Patients will be assigned a study ID that is linked only by a secure RedCap database. A study ID system utilizing patient initials and codes for dialysis facility will be employed to keep track of patients. Below is a chart outlining the various instruments that have been either developed or utilized for the purposes of this study:

Form Name	Summary	Study Group	Type	When to Be Administered
Chart Abstraction Eligibility Form	Chart review to gather demographic info and determine initial eligibility for study	Both	Data entry Form	Screening (via CDC medical record)
Screening Interview	Interview with patient to determine final eligibility for Phase 1 of the study	Both	Data entry Form	Screening

Phase 1 consent form	To consent patients to first phase of the study if eligible (1083 patients)	Both	Consent	After eligibility for study confirmed
Enrollment Checklist	Checklist to ensure completion of all baseline tasks	Both	Administrative Document	After baseline surveys are complete
Phase 2 consent form	To consent patients to second phase of the study if eligible (216 patients)	Both	Consent	After Mini reviewed and diagnosis of depression assessed

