USING LATENT VARIABLES AND DIRECTLY OBSERVED TREATMENT TO IMPROVE THE DIAGNOSIS AND MANAGEMENT OF DEPRESSION AMONG HEMODIALYSIS PATIENTS

Date: October 3, 2017

NCT Number: NCT03390933

Statistical analyses

Develop and validate hemodialysis-specific depression screening instrument. We will begin by using graphs and descriptive statistics to summarize demographic and medical characteristics as well as scores on our measures of depression (PHQ-9) and dialysis complications. Next, we will perform exploratory factor analysis of the nine PHQ-9 items to determine how many latent factors represent aspects of depression. It has been hypothesized that the PHQ-9 has a two factor structure representing somatic and affective domains of depression. However, our previous work on depression and multiple sclerosis suggested a single factor structure. We will use an oblique (geomin) rotation and will examine the eigenvalues, which represent the variance accounted for by each underlying factor, in a scree plot. The number of eigenvalues ≥ 1 represent unique latent factors. We will also use parallel analysis to calibrate our decisions regarding meaningful eigenvalues. This approach computes eigenvalues from a random dataset via Monte Carlo simulation with the same number of observations and variables as used in the factor analytics model. Further, we will use model fit criteria such as chi-square, comparative fit index (CFI), Tucker Lewis fit index (TLI), root mean square error of approximation (RMSEA), and standardized root mean square residual (SRMR) statistical test values to help determine the measurement properties of our latent constructs.

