Finally, we will use bootstrapping in order to validate our hdPHQ-9. After developing our model

based on the entire sample, we will fit the model on a series of bootstrap datasets (each by resampling with replacement the same number of observations as the entire sample). From this

procedure we will: 1) obtain the average (as well as the 95% confidence interval) for each of the model parameters and fit indices across the bootstrap samples and 2) observe how the extracted hdPHQ-9 factor scores for each individual in the original data set vary across the models derived from each bootstrapped sample. Thus, bootstrapping validation can be used to understand if there is any bias and sampling variation in the model parameters and associated hdPHQ-9 scores due to overfitting in the final model.

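### The primary outcome, 12-week remission, has no stated instrument or rule, and the SAP contains no analysis of the randomised comparison

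*Protocol*

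**What the plan says.** The protocol abstract gives a single primary outcome: "The primary outcome of the trial will be remission of depression at 12 weeks". It attaches no instrument, cut-off or rule.

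Under Study design overview and timetable, the protocol says "we will use the PHQ-9 and the DSM5 structured interview to screen for depression, confirm the diagnosis, and determine response to treatment". That sentence speaks of response rather than remission, and it does not rank or combine the two instruments. The same section says that at week 12 "patients in both groups will undergo repeat assessments of the PHQ-9, KDQOL, and DSM5 structured diagnostic interview", and then "These data will be used to address Aims B and C". Attachment A lists PHQ-9, KDQOL and MINI at the week-12 visit in both arms.

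A PHQ-9 score of 10 appears only as the threshold for going on to the diagnostic interview. The Data elements section treats the structured interview as the diagnostic gold standard, but does not make it the measure of the primary outcome.

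The SAP opens its analyses with "Develop and validate hemodialysis-specific depression screening instrument" and reaches its last step with "Finally, we will use bootstrapping in order to validate our hdPHQ-9". Between them it covers factor analysis, structural equation modelling and hdPHQ-9 scoring. It contains no comparison of fluoxetine with referral.

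On blinding, Data elements says "It is not possible to blind study personnel to assessments of depression treatment, adherence, response, and adverse effects during the trial", listing day 3 to week 10. No blinding is described for week 12.

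**The concern.** A trial with one primary outcome controls its error rate only if that outcome reduces to one variable and one test before results are seen. Here two variables qualify and no test is stated. The MINI yields presence or absence of disorder, while the PHQ-9 is a score that needs a cut-off to become remission. The two can classify the same patient differently at week 12.

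Three things are at stake. First, the error rate for the main claim is not fixed. Second, the treatment effect is not defined, because a difference in MINI remission and a difference in PHQ-9 remission are different quantities. Third, the SAP gives no analysis set, significance level, covariates or missing-data rule, so two analysts following it could report different primary results from the same data. Because personnel know the assignments, these choices should be closed in writing.

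**Working it through.** **1. The plan's own figure.** The trial size is 216, about 108 per arm (2 × 108 = 216). The documents give no significance level, power, control remission rate or target difference, so 216 can be neither reproduced nor called wrong. The nearest input is the expected fluoxetine result: 65% × 80% = 52% to 65% × 90% = 58.5%. That describes response, not remission.

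Power depends strongly on the control remission rate, which in turn depends on the remission rule. Assume a two-sided 5% level, 108 per arm and 52% on fluoxetine. Using the normal approximation with pooled variance under the null, for a control rate of 35%:

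- pooled rate 0.435; null standard error √(2 × 0.435 × 0.565 / 108) = 0.0675
- alternative standard error √((0.52 × 0.48 + 0.35 × 0.65) / 108) = 0.0665
- power = Φ((0.17 − 1.96 × 0.0675) / 0.0665) = Φ(0.57) ≈ 0.72

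The same formula gives 0.91 for a control rate of 30% and 0.42 for 40%. The control rates are assumptions.

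**2. False-positive rate if either instrument may carry the claim.** Inputs: two tests, each two-sided at 5% (assumed), critical value c = 1.96, test statistics bivariate normal with correlation ρ (assumed; the documents give none). With F the bivariate normal distribution function:

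- either direction: 1 − [F(c, c) − 2F(−c, c) + F(−c, −c)]
- favourable direction only: 1 − F(c, c)

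| ρ | F(c, c) | Favourable direction (nominal 0.025) | Either direction (nominal 0.05) |
|---|---|---|---|
| 0 | 0.9506 | 0.049 | 0.0975 |
| 0.5 | 0.9546 | 0.045 | 0.091 |
| 0.8 | 0.9610 | 0.039 | 0.078 |
| 0.9 | 0.9648 | 0.035 | 0.070 |
| 0.95 | 0.9677 | 0.032 | 0.065 |

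The last column is close to twice the one before it, because the two tests rarely reject in opposite directions. These figures count two candidate analyses only; alternative PHQ-9 cut-offs or combined rules would add to them.

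**3. Value of adjusting for baseline PHQ-9.** Assume 108 per arm, remission of 35% against 52% at the mean baseline score, a right-skewed baseline, and logistic regression with and without the baseline score. Over 1,500 simulated trials, power rose from 0.67 to 0.70 when one SD of baseline shifted the log-odds of remission by 0.5, and from 0.62 to 0.68 when it shifted them by 0.8. A repeat with 3,000 trials gave 0.67 to 0.69 and 0.62 to 0.67. The gain is about 2 to 6 points and rests wholly on the assumed prognostic strength.

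**4. Facilities.** 216 / 17 = 12.7, or about 13 randomised patients per facility.

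**5. Who assesses at week 12.** Data elements has a research assistant obtain the final PHQ-9 and KDQOL. Attachment A places the week-12 PHQ-9, KDQOL and MINI in the nurse practitioner's visit for fluoxetine and in the research assistant's visit for referral. On that reading, assessor type differs by arm for whichever instrument becomes primary, and for the PHQ-9 the two places disagree.

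**The case against.** The best reply is that the intended outcome can be read from the instruments' roles. The MINI establishes depression at entry, gives a yes-or-no diagnosis and is used only at baseline and week 12, while the PHQ-9 tracks patients between visits. Remission of MINI-confirmed depression is then the natural reading. That is fair, and it supports the MINI as the choice, but neither document states it, and the sentence on judging response names both instruments.

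A second reply is that the instruments will seldom disagree. The protocol says they address the same nine symptoms and correlate strongly, which favours the lower part of the error range. This stands, and is why the range extends to ρ = 0.9. It reduces the inflation but does not remove it.

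Third, some protocol text and the aims diagram were not in the copy reviewed, so a definition of remission there cannot be excluded. The SAP text is continuous, so the absence of the randomised comparison from it does not depend on that.

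Two stronger readings are tempting and not supported. A reader might infer that dialysis symptoms hold up PHQ-9 scores while sparing the MINI; the protocol says overlap may affect the accuracy of both. A reader might also infer that the team compares outcomes by arm every quarter. The quarterly review belongs to the safety monitoring plan, and nothing says that week-12 results are tabulated by arm.

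**Conclusion.** The point holds. The primary outcome lacks an operational definition in the supplied documents, two unranked instruments are available to supply one, and the SAP has no analysis of the randomised comparison. Under an assumed two-sided 5% level, freedom to choose between the two instruments gives a false-positive rate of about 7.0% to 9.1% for correlations of 0.9 to 0.5, or 3.5% to 4.5% against 2.5% in the favourable direction. The inflation is moderate, and it is conditional on the choice being made after outcomes are known. The documents permit that choice; they do not show that anyone intends it.

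A reader might go further and infer that the sample size is wrong, or that the hdPHQ-9 is a third candidate for the primary test. The first cannot be judged without the missing design inputs. On the second, the protocol calls it premature to use the new instrument for judging response before it has been assessed, so it is not counted here. The lost precision from not adjusting for baseline PHQ-9 is a secondary matter.

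**What to change.** Before outcome data by arm are examined, add a section to the SAP that states:

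- **Primary remission rule.** One instrument and one rule, for example MINI criteria for current depression no longer met at week 12, which matches the entry diagnosis. PHQ-9 remission, with its cut-off given, becomes secondary.
- **Analysis.** All randomised patients in their assigned arm; logistic regression adjusted for baseline PHQ-9, which is already collected; a single test at 0.05; the adjusted risk difference reported with its confidence interval.
- **Missing week-12 assessments.** A stated rule, for example multiple imputation using the PHQ-9 scores collected through week 10, with a sensitivity analysis.
- **Facility.** Adjustment is optional, given about 13 patients per facility; state the choice either way.

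In the protocol, reconcile Data elements with the two week-12 entries in Attachment A, so that the primary assessment is made by the same type of existing staff member in both arms. This matters most if the MINI is chosen, because Attachment A as written may give it a different type of assessor in each arm.

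The cost is SAP wording and a reallocation of week-12 tasks among existing staff; no new data are needed. The downside is that the sponsor gives up the later choice of instrument.

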### Study design overview and timetable

After a development and training period, we propose a cross-sectional study followed by a randomized controlled trial. The cross-sectional study will involve assessments of depressive symptoms (PHQ-9) and quality of life for **1083 patients**. These data will be used to address Aim A (diagram above). The trial will involve **216 patients** with DSM5-confirmed depression who will be assigned to **2 groups** using envelopes for randomization.

- Approximately 108 patients will be randomized into the intervention/fluoxetine group over the duration of the entire study. Patients randomized to fluoxetine will be prescribed 2 weeks of short-acting fluoxetine 20 mg and will be instructed to take the prescription daily for 2 weeks. After the approximately 2 weeks of daily fluoxetine is completed, patients will receive a filled prescription of long-acting fluoxetine 90 mg to be taken weekly (observed during dialysis) for 10 additional weeks. The first dose of fluoxetine 90mg will be 5-8 days after the last dose of daily 20mg fluoxetine based on FDA guidelines. During each week, the nurse practitioner or research assistant will review possible adverse effects and response to treatment. At the end of the 12-week study period, participants will be provided 4 additional weeks of 90 mg fluoxetine in order to provide sufficient time to follow up with their primary care physician or nephrologist.
- Approximately 108 patients will be randomized into the control/referral group over the duration of the study. Patients randomized to referral will be informed about their diagnosis and asked to follow-up with their nephrologists or primary care physicians and will also be given a list of nearby mental health providers. Details about their study

evaluation will be shared with their nephrologists, primary care physicians, and any mental health providers.

- After 12 weeks, patients in both groups will undergo repeat assessments of the PHQ-9, KDQOL, and DSM5 structured diagnostic interview. These data will be used to address Aims B and C.

We anticipate beginning the project at 2-3 dialysis facilities and estimate it will take about 4-5 months to complete the cross-sectional study and randomized controlled trial at these facilities. We will then involve another 2-3 facilities in the project. This process will continue until we reach our target sample size. Based on our previous work, we anticipate that it will take approximately 45 months to complete the trial. We considered involving more study personnel to shorten the time necessary to complete the trial but felt that this would impair our ability to maintain study quality and intervention fidelity. Intervention fidelity will be maintained through initial training, in-person meetings, monitoring of study notes, and direct observation. Trial results will be reported in accordance with CONSORT recommendations.

Note that we will use the PHQ-9 and the DSM5 structured interview to screen for depression, confirm the diagnosis, and determine response to treatment. While the overlap between dialysis complications and depressive symptoms may affect the accuracy of these methods, they are currently standard practice in depression intervention trials. **Until we have assessed the validity and responsiveness of the hemodialysis-specific PHQ-9 (hdPHQ-9), it would be premature to use this new instrument for screening or for determining response to treatment.**

Year	1	1	1	1	2	2	2	2	3	3	3	3	4	4	4	4	4	5	5	5
Quarter	1	2	3	4	1	2	3	4	1	2	3	4	1	2	3	4	1	2	3	4
DEVELOPMENT & TRAINING																				
Finalize study protocol, instruments	x	x																		
Train study personnel	x	x																		
Refine conceptual model	x	x																		
RANDOMIZED CONTROLLED TRIAL					x	x	x	x	x	x	x	x	x	x	x	x	x	x	x	
Recruit eligible patients			x	x	x	x	x	x	x	x	x	x	x	x	x	x	x	x	x	
Baseline evaluation		x	x	x	x	x	x	x	x	x	x	x	x	x	x	x	x	x	x	
Fluoxetine vs. referral trial		x	x	x	x	x	x	x	x	x	x	x	x	x	x	x	x	x	x	
Final evaluation		x	x	x	x	x	x	x	x	x	x	x	x	x	x	x	x	x	x	
ANALYSIS & MANUSCRIPTS																	x	x	x	x
Develop, validate new screening instrument																	x	x	x	x
Impact of directly observed weekly fluoxetine																		x	x	x
Responsiveness of new instrument																		x	x	x

